6.6.3.3.2 Treatment interruptions

For the definition of off-treatment periods an incomplete start or end date for a treatment interruption will be imputed the same way as specified for time-to-event analyses in [Section 6.6.2.2](#). For duration of interruption no imputation will be applied, i.e. interruptions with missing or incomplete start or end date will have duration missing. Overall duration of interruptions per subject will be missing in these cases as well.

6.7 BASELINE, TIME WINDOWS AND CALCULATED VISITS

As a general rule, the last assessment/measurement before or on the date of Visit 1 will be used as baseline.

Visit windowing will be performed as described in [Tables 6.7: 1, 6.7: 2](#) and [6.7: 3](#), in order to assign data to the relevant study visit based on the actual day of the assessment. Data will be analysed using the re-calculated visits in the statistical tables. However, in the listings, all visits performed will be displayed (even if outside time-window), along with the re-calculated visit. No time-windowing will be performed for the follow-up visit, i.e. follow-up visit will be displayed in listings (where applicable) whenever it was performed. A follow-up visit is only scheduled for subjects who prematurely discontinued nintedanib due to adverse event.

Table 6.7: 2 Time windowing rules for physical exam and vital signs

Time window of actual day ^[1]			Allocated to		
Start day	End day (included)	Length of the time-window [days]	Visit number	Visit name	Planned day of the visit
1	1	1	1	Baseline	1
2	22	21	2	2 weeks	15
23	43	21	3	4 weeks	29
44	71	28	4	8 weeks	57
72	127	56	5	12 weeks	85
128	211	84	6	24 weeks	169
212	295	84	7	36 weeks	253
296	379	84	8	48 weeks	337
380	463	84	9	60 weeks	421
464	547	84	10	72 weeks	505
548	631	84	11	84 weeks	589
632	715	84	12 (p)	96 weeks	673 (V _p)
$\frac{V_p + 1}{2} + \frac{V_{p+1} - V_p}{2}$	$\frac{V_{p+1}}{2} + \frac{V_{p+2} - V_{p+1}}{2}$	$\frac{V_{p+2} - V_p}{2}$	p + 1	...	$V_{p+1} = V_p + 12 \times 7$
...	Every 12 weeks thereafter	...

V_p denotes the planned day of the visit

[1] Date of Visit 1 in extension trial is taken into account as a reference to calculate time windows

Table 6.7: 3 Time windowing rules for laboratory measurements (and pregnancy test)

Time window of actual day ^[1]			Allocated to		
Start day	End day (included)	Length of the time-window [days]	Visit number	Visit name	Planned day of the visit
1	1	1	1	Baseline	1
2	22	21	2	2 weeks	15
23	43	21	3	4 weeks	29
44	71	28	4	8 weeks	57
72	106	35	5	12 weeks	85
107	148	42	5a ^[2]	18 weeks	127
149	190	42	6	24 weeks	169
191	232	42	6a ^[2]	30 weeks	211
233	274	42	7	36 weeks	253
275	316	42	7a ^[2]	42 weeks	295
317	379	63	8	48 weeks	337
380	463	84	9	60 weeks	421
464	547	84	10	72 weeks	505
548	631	84	11	84 weeks	589
632	715	84	12 _(p)	96 weeks	673 (V_p)
$\frac{V_p + 1}{2} + \frac{V_{p+1} - V_p}{2}$	$\frac{V_{p+1}}{2} + \frac{V_{p+2} - V_{p+1}}{2}$	$\frac{V_{p+2} - V_p}{2}$	$p + 1$...	$V_{p+1} = V_p + 12 \times 7$
...	Every 12 weeks thereafter	...

V_p denotes the planned day of the visit

^[1] Date of Visit 1 in extension trial is taken into account as a reference to calculate time windows

^[2] Intermediate lab tests ('a'-Visits) to be done as needed for additional safety monitoring at the discretion of the investigator and do not necessarily need to be a site visit.

If after windowing of visits at baseline, two values fall within the same baseline interval, then the last value will be taken into account. If after windowing of post-baseline visits, two visits fall in the same interval, then the measurement closest to the planned day of the visit will be taken into account. In case two measurements are equidistant from the planned day of the visit, then the last one will be picked.

7. PLANNED ANALYSIS

Unless otherwise specified, all analyses described in this section will be done on the Treated Set.

The labelling and display format of statistical parameters will follow BI standards (9). For End-Of-Text (EoT) tables, the set of summary statistics is: N / Mean / SD / Min / Median / Max. In descriptive statistics tables, mean, SD and median will be rounded to one additional digit than the raw individual value. In case some endpoints show some extreme data outside the expected range, quartiles and percentiles will be presented additionally.

Tabulations of frequencies for categorical data will include all possible categories and will display the number of observations in a category as well as the percentage (%) relative to the respective treatment group (unless otherwise specified, all subjects in the respective subject set whether they have non-missing values or not). The precision for percentages should be one decimal point. The category missing will be displayed only if there are actually missing values.

Unless otherwise specified, all analyses will be provided by randomised treatment group in the parent trial (Placebo or Nintedanib) and overall (Total column).

7.1 DEMOGRAPHIC AND OTHER BASELINE CHARACTERISTICS

A table in the CTR will present the number of subjects screened, entered and treated.

The completion status of subjects will be summarised by frequency counts with regards to planned treatment period as well as planned (trial) observation period together with corresponding reasons for non-completion. For potential interim analyses the number of subjects who are still ongoing in the trial will be presented in addition.

A similar summary will be provided regarding the first 48 weeks or the first 96 weeks only, i.e. until Week 48/Week 96 time point (Day 379/Day 715, i.e. 378/714 days after date of Visit 1).

Descriptive statistics as well as frequency counts will be provided for all demographic and baseline characteristics depicted in [Section 5.4.1](#).

7.2 CONCOMITANT DISEASES AND MEDICATION

Only descriptive statistics are planned for this section of the report.

7.2.1 Baseline conditions and cardiovascular medical history

Baseline conditions will be coded using the current Medical Dictionary for Regulatory Activities (MedDRA) version in use at BI at the time of (interim) database lock. They will be summarised by MedDRA system organ class (SOC) and preferred term (PT). The CTR table will show the counts of subjects with a baseline condition in each SOC (SOC sorted by standard European Medicines Agency (EMA) order) and then the conditions (preferred terms) under that SOC in descending order of overall prevalence (Total column).

The relevant cardiovascular medical history will be summarised, with particular focus on myocardial infarction, transient ischemic attacks, stroke, cardiac arrhythmia and heart failure.

7.2.2 Concomitant therapies

Concomitant therapies will be coded using the current World Health Organization Drug Dictionary (WHO-DD) version in use at BI at the time of (interim) database lock.

Concomitant therapies will be assigned to the following categories:

- Previous therapies: All therapies with a stop date before date of Visit 1 in extension trial.
- Baseline therapies: All therapies with a start date before date of first nintedanib intake in extension trial and a stop date after or on the day of Visit 1 in extension trial (or ongoing after completion of extension trial).
- On-treatment concomitant therapies: All therapies with a start date after or on the day of first nintedanib intake in extension trial and before or on the day of last nintedanib intake in extension trial.
- Post-study drug discontinuation therapies: All therapies with a start date after last nintedanib intake in extension trial and before or on the last contact as collected on the end of study eCRF page.

Concomitant therapies will be described over the entire duration of the extension trial. Similar summaries will be provided regarding the first 48 weeks or the first 96 weeks only, i.e. until Week 48/Week 96 time point (Day 379/Day 715, i.e. 378/714 days after date of Visit 1).

[Table 7.2.2: 1](#) and [Table 7.2.2: 2](#) summarise the concomitant therapy outputs which will be provided for analyses over the whole trial, over 48 weeks and over 96 weeks respectively, for each category of concomitant therapy created.

Summaries by Anatomical Therapeutic Chemical (ATC) classification and preferred name (PN) will use the ATC3 levels, and will be sorted by alphabetical ATC class and by decreasing order of overall prevalence (Total column) of PN within ATC class.

Summaries by Customised Drug Grouping (CDG) and PN will be sorted by alphabetical CDG name and by decreasing order of overall prevalence (Total column) of PN within CDG. CDGs are built using WHO-DD Standardised Drug Groupings (SDG), Sub-SDGs and ATC4 levels. CDGs are listed in [Section 9.2](#).

Table 7.2.2: 1 Concomitant therapy outputs over the whole trial

	By ATC and PN	By CDG and PN
Baseline therapies	X	X
On-treatment concomitant therapies	X	X
All baseline and on-treatment concomitant therapies	X	X
All baseline and on-treatment concomitant therapies with an incidence greater than 2% (in at least one treatment arm)	X	Not required
Post-study drug discontinuation therapies	Not required	Not required

Table 7.2.2: 2 Concomitant therapy outputs over 48 weeks and over 96 weeks

	By ATC and PN	By CDG and PN
Baseline therapies	Not required	Not required
On-treatment concomitant therapies	X	X
All baseline and on-treatment concomitant therapies	X	X
All baseline and on-treatment concomitant therapies with an incidence greater than 2% (in at least one treatment arm)	X	Not required
Post-study drug discontinuation therapies	Not required	Not required

7.3 TREATMENT COMPLIANCE

Only descriptive statistics are planned for this section of the report. The evaluations will be done over the whole trial. A similar summary will be provided regarding the first 48 weeks or the first 96 weeks only.

7.4 PRIMARY ENDPOINT

The primary objective of the trial is to assess the safety of Nintedanib, so please refer to [Section 7.8.1.4](#) for detailed analyses.

7.5 SECONDARY ENDPOINTS

This section is not applicable as no secondary endpoint has been specified in the protocol.

7.7 EXTENT OF EXPOSURE

Exposure will be summarised over the whole trial. Similar summaries will be provided regarding the first 48 weeks or the first 96 weeks only.

A summary table showing the duration on treatment in extension trial in months (both, mean and frequency in categories, see [Section 5.4.3](#)) will be presented together with duration of exposure in patient-years, total dose (mean) and dose intensity (both, mean and frequency in categories, see [Section 5.4.3](#)).

Besides, a summary table showing the duration on actual treatment dose in months (both, mean and frequency in categories, see [Section 5.4.3](#)) and off-treatment duration in weeks (mean) will be performed. This will take into account the actual dose following dose reductions or increases. Furthermore, the proportion of subjects on each dose actually taken as first dose in 1199-0248 will be presented.

A summary of dose reductions will be performed including number of subjects with at least one dose reduction, number of dose reductions (total and per subject) and reasons for dose reduction, as well as time to first dose reduction in extension trial (both, quartiles from Kaplan-Meier curve and frequency in categories, see [Section 5.3.3.3](#)). Dose intensity of subjects with at least one dose reduction will be summarised in addition. A similar summary will be performed for treatment interruptions. Additionally, the (total) duration of interruptions per subject will be summarised. For dose increases to 150 mg only number of subjects with at least one increase and total number of increases will be summarised.

Time to first dose reduction will only be calculated for subjects with first dose in extension trial 150 mg (see [Section 6.3](#) for further information on this analysis set).

As for the other exposure-related time-to-event analyses, time to premature treatment discontinuation and time to first dose reduction or treatment interruption will be summarised over the whole trial on the Treated Set according to both, quartiles from Kaplan-Meier curve and frequency in categories (see [Section 5.4.3.1.1](#)).

Separate Kaplan-Meier plots will be presented by randomised treatment group in the parent trial (Placebo or Nintedanib) and overall (total group) for all exposure-related time-to-event analyses. No statistical tests will be performed. Kaplan-Meier plots present data over the whole trial. Kaplan Meier estimates and confidence intervals (using Greenwood variance formula) for the cumulated time-to-event rate will be calculated at 48 weeks (378 days after date of first nintedanib intake), at every further 48 weeks (336 days) and over the whole trial.

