5.4.3.1.1 Exposure-related time-to-event analyses

Exposure-related time-to-event analyses will be performed for the following items:

- Time to first dose reduction [days]
- Time to first treatment interruption [days]
- Time to premature treatment discontinuation [days]
- Time to first dose reduction or treatment interruption [days]

Time-to-event [days] for exposure-related analyses is derived based on first nintedanib intake in extension trial as

$$\textit{Date of event/censoring} - \textit{Date of first nintedanib intake} + 1 \text{ day}$$

For the above mentioned time-to-event analyses subjects with no such event occurred during the extension trial will be censored according to the mechanism for censoring as described in [Table 5.4.3.1.1: 1.](#)

These time-to-event analyses will also be summarised in categories:

- <=1 month (31 days)
- >1 to <=3 months (91 days)
- >3 to <=6 months (182 days)
- >6 to <=12 months (365 days)
- >12 to <=18 months (547 days)
- >18 to <=24 months (730 days)
- >24 to <=36 months (1095 days)
- >36 months
- Censored

Further categories might be defined if needed.

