5.4.4.1 Time-to-event analyses for liver enzyme elevations

Time to first occurrence in extension trial of the above described liver enzyme elevations [days] will be analysed as

Date of event/censoring - Date of first nintedanib intake + 1 day

Subjects with no such event occurred during the trial will be censored according to the mechanism for censoring as described in [Table 5.4.4.1: 1](#).

These times to onset of first event in extension trial will also be summarised in categories:

- <=1 month (31 days)
- >1 to <=3 months (91 days)
- >3 to <=6 months (182 days)
- >6 to <=12 months (365 days)
- >12 to <=18 months (547 days)
- >18 to <=24 months (730 days)
- >24 to <=36 months (1095 days)
- >36 months
- Censored

Further categories might be defined if needed.

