7.8.1.3 Adverse events with additional information collection

Diarrhoea, bleeding and ILD are AEs with additional AE-specific information collected on the eCRF. These are investigator reported on the eCRF and will be identified using this information for this analysis. That is if the diarrhoea information has been completed for an adverse event then the adverse event will be considered as diarrhoea for this analysis regardless of subsequent MedDRA coding of the verbatim term. Likewise, if the bleeding information has been completed for an adverse event then the adverse event will be considered as bleeding for this analysis regardless of subsequent MedDRA coding of the verbatim term. The same applies to ILD.

The frequency of subjects with AEs with additional information collection will be summarised by randomised treatment group in the parent trial (and overall), primary SOC and

PT separately for diarrhoea, bleeding and ILD. The additional information collected will also be summarised at the AE level (occurrence level) rather than at the subject level separately for diarrhoea, bleeding and ILD.

For the time to first onset of diarrhoea, bleeding or ILD, respectively, in extension trial Kaplan-Meier plots by treatment will be created. The same censoring rules and categories as for time to first liver enzyme elevation in extension trial will be used. See [Section 5.4.4.1](#) for details.

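### Kaplan-Meier cumulated rates for first dose reduction, first treatment interruption and their composite will overstate the proportion of patients affected if death and premature permanent discontinuation are censored

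*SAP*

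**What the plan says.** SAP 7.7 plans Kaplan-Meier plots "for all exposure-related time-to-event analyses". There are four of these: first dose reduction (only in patients who start the extension on 150 mg), first treatment interruption, premature treatment discontinuation, and first reduction or interruption. The same paragraph adds that "Kaplan Meier estimates and confidence intervals (using Greenwood variance formula) for the cumulated time-to-event rate will be calculated at 48 weeks" (378 days after first intake), then "at every further 48 weeks (336 days) and over the whole trial".

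SAP 5.4.3.1.1 gives the rule for patients without an event: "subjects with no such event occurred during the extension trial will be censored according to the mechanism for censoring" set out in Table 5.4.3.1.1: 1. That table is not in the text available for review, which is not a fault in the plan. The summary categories in the section have one non-event class, Censored. No competing-event estimator is named.

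Other events get less. For liver enzyme elevation, SAP 7.8.2.2 plans Kaplan-Meier quartiles, category frequencies and a plot. For diarrhoea, bleeding and ILD, SAP 7.8.1.3 says that "in extension trial Kaplan-Meier plots by treatment will be created" and that "The same censoring rules and categories as for time to first liver enzyme elevation in extension trial will be used". Neither section plans a cumulated rate at fixed times.

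SAP 7.7 also reports the number of subjects with at least one dose reduction, with a similar summary for interruptions.

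**The concern.** Dose reduction and interruption can happen only to a patient who is alive and still on treatment. Kaplan-Meier treats a censored patient as still able to have the event later, at the same rate as those who remain. After death or a permanent stop that is untrue.

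The protocol also links stopping to the same toxicity. Section 4.2.1 offers reduction or interruption to manage adverse events, and in some circumstances asks that permanent discontinuation be considered instead. Stopping is thus partly an alternative outcome of the same process rather than unrelated loss.

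At stake is how a figure labelled as a cumulated rate at 48 or 96 weeks will be understood. Most readers will take it as the proportion of patients who needed a reduction or interruption by then. The error is upward and, in the constant-hazard illustration below, grows over the planned time points. The report could also show a crude count and a higher cumulated rate for the same event without explaining the difference.

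**Working it through.** **No figure to reproduce.** The plan states no event, death or discontinuation rate for the extension. Its time points are consistent: 378 + 336 = 714 days, which is the Week 96 time point in SAP 5.4.3.2. The next is 714 + 336 = 1050 days.

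**Formulas.** Assume constant, independent hazards: *h* for the event, *c* for exit by death or premature permanent stop, *t* in years.

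- One minus Kaplan-Meier, exits censored: 1 − exp(−*ht*)
- Proportion of patients with the event: *h*/(*h* + *c*) × [1 − exp(−(*h* + *c*)*t*)]

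The second is never above the first, so the direction does not depend on the values chosen.

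**Exit hazard (assumed).** The only anchor is the parent trial: 663 randomised (protocol 1.2) and about 480 expected to complete on treatment (protocol 3.1), so 480/663 = 72.4%. With an assumed mean time in the parent trial of 1.0, 1.3 or 1.6 years, −ln(480/663)/time = 0.323, 0.248 or 0.202 per year. The 480 is a planning estimate and extension patients are selected completers, so lower values, down to 0.05, are included.

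**Event hazard (assumed).** 0.15 to 0.5 per year.

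**Worked case**, *h* = 0.3 and *c* = 0.2, at day 714 (*t* = 714/365.25 = 1.955):

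- 1 − exp(−0.3 × 1.955) = 44.4%
- 0.3/0.5 × [1 − exp(−0.5 × 1.955)] = 0.6 × 0.624 = 37.4%

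The same case gives 26.7% against 24.2% at day 378, and 57.8% against 45.7% at day 1050.

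**Range at day 714**, one minus Kaplan-Meier against the proportion affected:

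| Exit hazard per year | *h* = 0.15 | *h* = 0.3 | *h* = 0.5 |
|---|---|---|---|
| 0.05 | 25.4% v 24.3% | 44.4% v 42.5% | 62.4% v 59.9% |
| 0.1 | 25.4% v 23.2% | 44.4% v 40.7% | 62.4% v 57.5% |
| 0.2 | 25.4% v 21.2% | 44.4% v 37.4% | 62.4% v 53.2% |
| 0.3 | 25.4% v 19.5% | 44.4% v 34.5% | 62.4% v 49.4% |

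The gaps are 1.1 to 2.5 points in the first row and 2.2 to 13.0 points in the other three. A simulation of 480 patients (2000 runs) at another setting, a 22.6% one-year event rate and *c* = 0.216 per year, gave 39.4% against an actual 32.7% at day 714, as the formulas predict.

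**Does the censoring date matter?** Yes. If patients who die or stop stay in the risk set to their administrative end, one minus Kaplan-Meier equals the proportion affected. Two sections make that unlikely. The opening of SAP 5 gives time-to-event analyses as an example of where the derived last contact date (when the patient was known to be alive) is used. Protocol 6.2.3 makes the end-of-treatment visit the completion visit, or the follow-up visit 28 days after last intake for a stop due to adverse events. Even a 28-day delay is only 28/714 = 3.9% of the period to Week 96.

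**The case against.** The best defence has four parts.

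- **The censoring table cannot be seen.** This stands as a reservation: if it keeps such patients at risk to their administrative end, the point falls away.
- **Actual proportions are already planned.** SAP 7.7 counts patients with a reduction or interruption, and SAP 5.4.3.1.1 tabulates first-event times by interval. Adding up those intervals roughly gives the crude cumulative proportion while few patients have been administratively censored. This stands and lowers the priority. It does not correct the fixed-time figures, and the interval limits (365, 547 and 730 days) do not match days 378 and 714.
- **Risk while on treatment is a legitimate target.** This stands as a choice of estimand, but the SAP does not label the figures that way, and the reading depends on stops being unrelated to the event.
- **The size is assumed.** This stands; only the direction is firm.

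A reader might infer more than the documents support. One might extend the fixed-time rates to liver elevation, diarrhoea, bleeding and ILD, but SAP 7.7 limits them to the exposure analyses. A permanent stop does not prevent those four events either; it competes only if the target is on-treatment events. One might see these curves as the main account of tolerability, but SAP 7.8.1.4 bases the primary endpoint on frequencies and exposure-adjusted rates. One might expect cumulative incidence to put the two parent-trial groups on one scale, but it too depends on each group's exit rate.

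**Conclusion.** The point holds for first dose reduction, first interruption and their composite. With death and premature permanent stop censored at or near the time they occur, the planned cumulated rate is not the proportion of patients affected and overstates it.

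The true size cannot be found from the documents. Under constant independent hazards and event hazards of 0.15 to 0.5 per year, the Week 96 overstatement is about 1 to 3 points at an exit hazard of 0.05 per year and about 2 to 13 points at 0.1 to 0.3 per year. The conclusion assumes that the unseen censoring table does not hold such patients in the risk set.

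The documents do not support replacing Kaplan-Meier throughout the SAP. For liver elevation, diarrhoea, bleeding and ILD, clear labelling is enough. Premature discontinuation is outside the point, because there stopping is itself the event. All these analyses are descriptive, crude counts are planned and the primary endpoint is untouched, so this is an improvement of low to moderate priority.

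**What to change.** In SAP 5.4.3.1.1 and 7.7, add Aalen-Johansen cumulative incidence with confidence intervals, at the time points already planned, for first dose reduction, first interruption and their composite. Treat death and premature permanent discontinuation as competing events. Censor only administrative ends: planned completion or a move to nintedanib supplied outside the trial, and data cut-off. Label any retained one-minus-Kaplan-Meier figure as conditional on remaining on treatment.

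In SAP 5.4.4.1, 7.8.1.3 and 7.8.2.2, label the curves and quartiles for liver elevation, diarrhoea, bleeding and ILD as risk while on treatment, or show on-treatment cumulative incidence. Do not describe them as the proportion of patients affected.

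The cost is SAP wording, a small programming change and slightly more output, with no new data. The new figures will not be directly comparable with Kaplan-Meier figures from the parent trial; keeping the labelled Kaplan-Meier figures beside them preserves that comparison.
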